1.1. Synopsis

Protocol Title: An Open-label, Two-part Study of the Disposition and Absolute Bioavailability of [¹⁴C]-LY3484356 in Healthy Females of Non-Childbearing Potential

Short Title: Two-part Study of the Disposition and Absolute Bioavailability of [¹⁴C]-LY3484356

Rationale: Study J2J-MC-JZLE (JZLE) is a Phase 1 open-label, 2-part study of LY3484356 containing [¹⁴C]-LY3484356 administered to healthy females of non-childbearing potential.

Part 1 of this study determines the disposition of [¹⁴C]-LY3484356 and identifies the metabolites present in plasma, urine, and feces following a single oral administration of LY3484356 containing [¹⁴C]-LY3484356 as a solution. This study will provide understanding of the clearance pathways of LY3484356 in humans, which is important to assess the likelihood of effects of renal or hepatic impairment on the disposition of LY3484356 and the likelihood for drug-drug interactions (DDIs) with LY3484356. Furthermore, knowledge of the metabolism and elimination of parent drug and its metabolites and major circulating metabolites is useful for evaluating needs of metabolite(s)-mediated DDI studies and metabolite(s) in safety testing requirements elucidated in the Food and Drug Administration Guidance and International Conference on Harmonisation M3.

Part 2 of this study determines the absolute bioavailability of LY3484356 of a tablet formulation in humans using an intravenous (IV) microtracer of [¹⁴C]-LY3484356 (containing CCI radioactivity). Absolute bioavailability information aids quantitative evaluation of drug disposition of LY3484356.

Objectives and Endpoints:

Part 1

Objectives	Endpoints
Primary	

To determine the disposition of radioactivity in healthy nonchildbearing women following oral administration of a single dose of CCI [sup>14]C-LY3484356	
Urinary and fecal excretion of total radioactivity over time expressed as a percentage of the total radioactive dose

Secondary	

 • To determine the pharmacokinetics (PK) of total radioactivity and LY3484356 in plasma following a single oral dose of [CC1] [14C]-LY3484356 • To assess the mass balance by quantifying radioactivity excretion in urine, feces, and expired air (if applicable) • To identify metabolites of LY3484356 in plasma, urine, and feces • To assess the safety and tolerability of a single dose of [CC1] [14C]-LY3484356 (containing 100 μCi) in healthy nonchildbearing women 	
AUC(0-∞) and C_{max} for radioactivity and LY3484356 in plasma
 
 • Total radioactivity recovered in urine, feces, and expired air (if applicable) • Total number of metabolites and identification of metabolites • A summary of TEAEs

Part 2

Objectives	Endpoints
Primary	

 • To determine the absolute bioavailability of LY3484356 following a single oral dose of [CC1] of LY3484356 along with an IV dose of [CC1] of [14C]-LY3484356 [CC1] 	
 • absolute bioavailability (F) of LY3484356
Secondary	

 • To evaluate the PK of LY3484356, [14C]-LY3484356 and total radioactivity following oral dosing of LY3484356 and IV dosing of [14C]-LY3484356 • To assess the safety and tolerability of LY3484356 following a single oral dose of [CC1] LY3484356 along with an IV dose of [CC1] of [14C]-LY3484356 [CC1] in healthy nonchildbearing women 	
 • AUC(0-∞) and C_{max} for total radioactivity, [14C]-LY3484356 and LY3484356 in plasma • A summary of TEAEs

Overall Design:Screening (Part 1 and Part 2)

All participants will be screened within 28 days prior to enrollment.

Treatment and Assessment Period*Part 1:*

Participants will be admitted to the Clinical Research Unit (CRU) on Day -1. On the morning of Day 1, following an overnight fast of at least 10 hours, participants will receive a single oral dose of CCI of [¹⁴C]-LY3484356 CCI administered as an oral solution.

Participants will be discharged from the CRU as early as Day 12 and up to Day 22, provided recovery of radioactivity has reached the following threshold values:

- $\geq 90\%$ of the radioactive dose is recovered, and
- $\leq 1\%$ of the radioactive dose per day is recovered in excreta (urine and feces combined) for 2 consecutive days on which a fecal sample is collected.

Sample collection and CRU confinement will continue until discharge criteria are met or the maximum stay is reached, unless otherwise agreed upon by the sponsor and investigator (or designee).

For participants experiencing emesis within 4 hours following ¹⁴C dosing, vomitus will be collected. Attempts will be made to collect vomitus from participants experiencing emesis after 4 hours post dose. All vomitus will be collected and stored for possible analysis as deemed appropriate.

Part 2:

Participants will be admitted to the CRU on Day -1. On the morning of Day 1, following an overnight fast of at least 10 hours, participants will receive a single oral dose of CCI of LY3484356 as CCI tablets and followed CCI by a single dose of CCI of [¹⁴C]-LY3484356 (containing CCI of radioactivity [microtracer]) administered as approximately a CCI IV infusion. Participants will remain resident in the CRU until Day 9.

During the infusion and for at least 2 hours post-infusion, the blood samples will be taken from the arm contra-lateral to the infusion site.

Follow-up (Part 1 and Part 2)

Participants will receive a follow-up call approximately 7 days after clinic discharge.

Disclosure Statement: This study is an open-label, 2-part, disposition and absolute bioavailability study of [¹⁴C]-LY3484356 in healthy females with non-childbearing potential at a single Phase 1 Clinical Research Unit (CRU).

Number of Participants: In Part 1, it is planned that up to 6 participants may be enrolled to ensure that at least 4 participants complete the study or have evaluable PK data; in Part 2, it is planned that up to 8 participants may be enrolled to ensure that at least 6 participants complete the study or have evaluable PK data for both treatments (oral and IV). Participants in Part 1 will

not participate in Part 2, nor will participants in Part 2 participate in Part 1. Part 1 and Part 2 are independent of each other and do not need to be conducted in sequential order.

Intervention Groups and Duration: Participants in Part 1 participate in 1 treatment period. Participants in Part 1 will be screened within 28 days prior to enrollment and will receive a single oral dose of CCI of [¹⁴C]-LY3484356 (containing CCI).

Participants in Part 2 will participate in 1 treatment period. Participants in Part 2 will be screened within 28 days prior to enrollment and will receive a single oral dose of CCI of LY3484356 followed 4 hours later by a single dose of CCI of [¹⁴C]-LY3484356 (containing CCI of radioactivity [microtracer]).

Participants in both study parts will receive a follow-up phone call approximately 7 days after discharge from the study site.

The study duration for participants in each cohort is expected to be as follows:

- **Part 1:** up to 59 days
- **Part 2:** up to 46 days

Data Monitoring Committee: No

CCI

CCI

CCI

CCI

CCI

CCI

CCI

2. Introduction

LY3484356 is an orally bioavailable, non-covalent, selective estrogen receptor degrader (SERD) in development for the treatment of breast cancer and endometrial cancer (EC). It is a potent degrader and selective antagonist of wild-type and mutant estrogen receptor α (ER α or ESR1).

Full details of the preclinical safety, efficacy, and pharmacokinetics (PK), and clinical PK may be found in the Investigator's Brochure (IB).

2.1. Study Rationale

Study J2J-MC-JZLE (JZLE) is a Phase 1 open-label, 2-part study of LY3484356 containing [^{14}C]-LY3484356 administered to healthy females of nonchildbearing potential.

Part 1 of this study determines the disposition of [^{14}C]-LY3484356 and identifies the metabolites present in plasma, urine, and feces following a single oral administration of LY3484356 containing [^{14}C]-LY3484356. This provides understanding of the clearance pathways of LY3484356, which is important to assess the likelihood of effects of renal or hepatic impairment on the disposition of LY3484356 and the likelihood for drug-drug interactions (DDIs) with LY3484356. Furthermore, knowledge of the metabolism and elimination of parent drug and its metabolites and major circulating metabolites is useful for evaluating needs of metabolite(s)-mediated DDI studies and metabolite(s) in safety testing requirements elucidated in the Food and Drug Administration Guidance and International Conference on Harmonisation M3.

Part 2 of this study determines the absolute bioavailability of LY3484356 of a tablet formulation in humans using an intravenous (IV) microtracer of [^{14}C]-LY3484356 (containing CCI radioactivity). Absolute bioavailability information aids quantitative evaluation of drug disposition of LY3484356 and subsequent planning and designing of additional clinical pharmacology studies.

2.2. Background

[figure not shown]
Breast cancer is the most frequent cancer among women and is a major cause of cancer-related deaths worldwide. It is estimated that more than 2 million new cases of breast cancer occurred worldwide in women in 2018 (Bray et al. 2018). Treatment options for women with breast cancer are largely determined by tumor HR and HER2 status (NCCN 2018; Waks and Winer 2019), and over 2 thirds of breast cancers express estrogen receptor (ER) - a key driver of breast cancer initiation and progression. For patients with advanced HR+/HER2-status, treatment includes endocrine therapy (ET) (e.g., tamoxifen, anastrozole, letrozole, fulvestrant) alone or in combination with cyclin-dependent kinase (CDK)4 and 6 inhibitors as indicated (e.g., abemaciclib, palbociclib, or ribociclib), as well as standard chemotherapy (e.g., capecitabine, docetaxel, paclitaxel, nab-paclitaxel [NCCN 2018; Waks and Winer 2019]). For patients with advanced HR+/HER2+status, treatment includes HER2-directed therapies e.g., trastuzumab, pertuzumab, or trastuzumab emtansine administered alone and in combination with other HER2-directed therapies, chemotherapy, or ET.

In most ER+ breast cancers, ER is an important therapeutic target even after development of resistance to endocrine therapies (Weatherman et al. 1999; Baselga et al. 2012; Turner et al. 2015; Finn et al. 2016; André et al. 2019). SERDs are one of the treatment options for estrogen receptor-positive (ER+)/human epidermal growth factor receptor 2-negative (HER2-) breast cancer patients. Fulvestrant is currently the only regulatory agency-approved SERD for the treatment of ER+ metastatic breast cancer (mBC) (Nardone et al. 2019). Its efficacy is highly dose-dependent, where increasing the administered dose led to improved survival (Di Leo et al. 2014). However, the intramuscular (IM) route of fulvestrant administration limits the amount of fulvestrant that can be given to patients. Several studies have shown that with the current maximum feasible dose, fulvestrant treatment is not able to completely degrade ER in patients and can be associated with early progression (van Kruchten et al. 2015). Thus, there is unmet medical need to develop oral SERDs with higher bioavailability, greater ER targeting, and degradation efficiency (Nardone et al. 2019).

Endometrial cancer, while less frequently diagnosed than breast cancer, is increasing worldwide. In the United States, the incidence of EC has increased by approximately 12,000 cases between 2013 and 2019 (Howlader et al. 2020). Endometrioid EC represents about 80% of EC cases, and overexpression of estrogen may contribute to tumor proliferation (Ellenson et al. 2011).

Patients with ER+ breast cancer have several treatment options. However, at the time of progression on ET, the disease becomes less responsive, and options are often limited to chemotherapy. Mutations in ESR1 can lead to an estrogen independent activation of ER pathway, driving tumor growth and resistance to commonly used estrogen deprivation strategies (eg, aromatase inhibitors). Mutant ER α mutant ER+, HER2- breast cancers are potentially amenable to therapy with LY3484356 based on preclinical data. Additionally, for ER+, HER2+ breast cancers, after progression on prior HER2 directed therapies, chemotherapy, and type 1 diabetes mellitus, clinical evidence supports the administration of fulvestrant, a SERD, in combination with trastuzumab (Robertson et al. 2010). The clinical benefit in this patient population could potentially be further improved with the use of LY3484356 as SERD.

A large, bold, red rectangular box redacts the text "CCI".

2.2.2. Clinical Pharmacokinetics

Pharmacokinetic data from cancer patient studies showed that maximal plasma concentrations were reached approximately 4 hours post dose with an elimination half-life of approximately 25 to 30 hours. Increases in exposures were also observed from 200 to 1200 mg QD in patient studies and were approximately dose proportional. Additional content is described in Section 5.1.1 in the IB.

A large, bold, red rectangular box redacts the text "CCI".

2.3. Benefit/Risk Assessment

LY3484356 is a potent antagonist and degrader of ER α and has demonstrated significant activity in preclinical models against ER wild-type and mutant tumors. There is no anticipated benefit for the healthy participants in this study.

A large, bold, red rectangular box redacts the text "CCI".

CCI

CCI

3. Objectives and Endpoints

Part 1

Objectives	Endpoints
Primary	

 To determine the disposition of radioactivity in healthy nonchildbearing women following oral administration of a single dose of CCI [14C]-LY3484356 	
 Urinary and fecal excretion of total radioactivity over time expressed as a percentage of the total radioactive dose
Secondary	

 To determine the pharmacokinetics (PK) of total radioactivity and LY3484356 in plasma following a single oral dose of CCI [14C]-LY3484356 To assess the mass balance by quantifying radioactivity excretion in urine, feces, and expired air (if applicable) To identify metabolites of LY3484356 in plasma, urine, and feces To assess the safety and tolerability of a single dose of CCI [14C]-LY3484356 CCI in healthy nonchildbearing women 	
 AUC(0-∞) and C_{max} for radioactivity and LY3484356 in plasma Total radioactivity recovered in urine, feces, and expired air (if applicable) Total number of metabolites and identification of metabolite A summary of TEAEs

Part 2

Objectives	Endpoints
Primary	

 To determine the absolute bioavailability of LY3484356 following a single oral dose of CCI of LY3484356 along with an IV dose of CCI of [14C]-LY3484356 CCI 	
 absolute bioavailability (F) of LY3484356

Secondary	

• To evaluate the PK of LY3484356, [¹⁴C]-LY3484356, and total radioactivity following oral dosing of LY3484356 and IV dosing of [¹⁴C]-LY3484356• To assess the safety and tolerability of LY3484356 following a single oral dose of CCI LY3484356 along with an IV dose of CCI of [¹⁴C]-LY3484356 CCI in healthy nonchildbearing women	
• AUC(0-∞) and C_{max} for total radioactivity, [¹⁴C] LY3484356, and LY3484356 in plasma• A summary of TEAEs

Abbreviations: AUC_{0-∞} = area under the concentration-time curve from time 0 extrapolated to infinity; C_{max} = maximum observed concentration; F = absolute bioavailability (LY3484356 only); TEAE = treatment-emergent adverse event.

4. Study Design

4.1. Overall Design

Study JZLE is an open-label, 2-part, disposition and absolute bioavailability study of [¹⁴C]-LY3484356 in healthy females with nonchildbearing potential at a single Phase 1 CRU. In Part 1, it is planned that up to 6 participants may be enrolled to ensure that at least 4 participants complete the study or have evaluable PK data. In Part 2, it is planned that up to 8 participants may be enrolled to ensure that at least 6 participants complete the study or have evaluable PK data for both treatments (oral and IV). Participants in Part 1 will not participate in Part 2, nor will participants in Part 2 participate in Part 1. Part 1 and Part 2 are independent of each other and do not need to be conducted in sequential order.

The schemata in Section 1.2 illustrate the study design.

Safety assessments, including AEs, clinical laboratory tests, vital signs, and ECGs, and blood sampling for PK, will be performed according to the SoA (Section 1.3).

4.1.1. Screening (Part 1 and Part 2)

All participants will be screened within 28 days prior to enrollment.

4.1.2. Treatment and Assessment Period

Part 1:

Participants will be admitted to the CRU on Day -1. On the morning of Day 1, following an overnight fast of at least 10 hours, participants will receive a single oral dose of CCI of [¹⁴C]-LY3484356 CCI administered as an oral solution.

Participants will be discharged from the CRU as early as Day 12 and up to Day 22, provided recovery of radioactivity has reached the following threshold values:

- ≥90% of the radioactive dose is recovered, and
- ≤1% of the radioactive dose per day is recovered in excreta (urine and feces combined) for 2 consecutive days on which a fecal sample is collected.

Sample collection and CRU confinement will continue until discharge criteria are met or the maximum stay is reached, unless otherwise agreed upon by the sponsor and investigator (or designee).

For participants experiencing emesis within 4 hours following ¹⁴C dosing, vomitus will be collected. Attempts will be made to collect vomitus from participants experiencing emesis after 4 hours post dose. All vomitus will be collected and stored for possible analysis as deemed appropriate.

Part 2:

Participants will be admitted to the CRU on Day -1. On the morning of Day 1, following an overnight fast of at least 10 hours, participants will receive a single oral dose of CCI of LY3484356 as CCI tablets and followed CCI later by a single dose of CCI of [¹⁴C]-LY3484356 (containing CCI of radioactivity [microtracer]) administered as approximately a CCI IV infusion. Participants will remain resident in the CRU until Day 9.

During the infusion and for at least 2 hours post-infusion, the blood samples will be taken from the arm contra-lateral to the infusion site.

4.1.3. Follow-up (Part 1 and Part 2)

Participants will receive a follow-up call approximately 7 days after clinic discharge.

4.2. Scientific Rationale for Study Design

This study has an open-label design because the study endpoints are not considered subjective. This study also has no control treatment which is standard and widely used in radiolabeled studies.

In Parts 1 and 2, oral administration has been chosen since this is the intended clinical route of LY3484356 administration.

The IV microtracer method to be used in Part 2 allows for simultaneous oral and IV dosing in the same participants, which is expected to result in less variability in absolute bioavailability estimates as the systemic clearance is equivalent for the IV and oral doses.

Analysis of urine and fecal concentrations of [¹⁴C]-LY3484356 and total radioactivity will allow for determination of the amount and percentage of LY3484356 excreted unchanged in urine and feces.

Conducting the study in healthy participants will allow the evaluation of LY3484356 disposition and bioavailability in the absence of concomitant medications and comorbidities. Healthy females of nonchildbearing potential have been selected as the study population since the pharmacologic mechanism of LY3484356 is to degrade the ER, and effects on the female reproductive organs are expected (see Section 2.3).

The doses, participant population, study duration, and sample collection timing are considered adequate to achieve the study objectives.

4.3. Justification for Dose

4.3.1. LY3484356

CCI

4.3.2. Radioactive Dose

For Part 1, the planned radioactive dose of CCI of [¹⁴C]-LY3484356 CCI is expected to provide a sufficient radioactive signal to achieve the study objectives with minimal radiation risk to participants.

4.4. End of Study Definition

A participant is considered to have completed the study if she has completed all scheduled procedures shown in the SoA (Section 1.3).

The end of the study is defined as the date of the last follow-up phone call for the last participant in the study.

5. Study Population

Eligibility of participants for enrollment in the study will be based on the results of medical history, physical examination, vital signs, clinical laboratory tests, and ECG.

The nature of any conditions present at the time of the physical examination and any pre-existing conditions will be documented.

Prospective approval of protocol deviations to recruitment and enrollment criteria, also known as protocol waivers or exemptions, is not permitted.

5.1. Inclusion Criteria

Participants are eligible to be included in the study only if all of the following criteria apply:

Age

1. Participant must be 18 to 65 years of age inclusive, at the time of signing the informed consent.

Type of Participant

2. Participants who are overtly healthy as determined by medical assessment including medical history, physical examination, laboratory tests, 12-lead ECG, and vital signs.
3. Participants who have clinical laboratory test results within the normal reference range for the population or investigative site, or results with acceptable deviations that are judged to be not clinically significant by the investigator.
4. Participants who have venous access sufficient to allow for blood sampling as per the protocol.
5. Participants who have a history of a minimum of 1 bowel movement per day (Part 1 only).

Weight

6. Body mass index within the range 18.0 to 35.0 kg/m² (inclusive).

Sex

7. Female participants of nonchildbearing potential. This includes females who are not pregnant, non-lactating and either:
 - Infertile due to surgical sterilization (hysterectomy, bilateral oophorectomy or bilateral salpingectomy, bilateral tubal ligation, or bilateral tubal occlusion), or alternate medical cause/congenital anomaly (e.g., Müllerian agenesis). For individuals with permanent infertility due to an alternate medical cause/congenital anomaly, investigator discretion should be applied to determining study entry.
or
 - Postmenopausal (see Appendix 4 [Section 10.4] for details)

Informed Consent

8. Capable of giving signed informed consent as described in Appendix 1, which includes compliance with the requirements and restrictions listed in the informed consent form (ICF) and in this protocol.

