8.2.4. Clinical Safety Laboratory Assessments

See Appendix 2 (Section 10.2) for the list of clinical laboratory tests to be performed and the SoA (Section 1.3) for the timing and frequency.

The investigator must review the laboratory results, document this review, and report any clinically relevant changes occurring during the study as an AE. The laboratory results must be retained with source documents unless a Source Document Agreement or comparable document cites an electronic location that accommodates the expected retention duration.

All laboratory tests with values considered clinically significantly abnormal during participation in the study should be repeated until the values return to normal or baseline or are no longer considered clinically significant by the investigator, CP, or CRP.

- If such values do not return to normal/baseline within a period of time judged reasonable by the investigator, the etiology should be identified and the sponsor notified.
- All protocol-required laboratory assessments, as defined in Appendix 2 (Section 10.2), must be conducted in accordance with the SoA and standard collection requirements.

If laboratory values from non-protocol specified laboratory assessments performed at an investigator-designated local laboratory require a change in participant management or are considered clinically significant by the investigator (e.g., SAE or AE or dose modification), then report the information as an AE.

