10.2. Appendix 2: Clinical Laboratory Tests

The tests detailed below will be performed by the local laboratory.

Protocol-specific requirements for inclusion or exclusion of participants are detailed in Section 5 of the protocol.

Additional tests may be performed at any time during the study as determined necessary by the investigator or required by local regulations.

Investigators must document their review of the laboratory safety results.

Clinical Laboratory Tests

Hematology

Hematocrit
Hemoglobin
Erythrocyte count (RBC)
Mean cell volume
Mean cell hemoglobin
Mean cell hemoglobin concentration
Leukocytes (WBC)
Platelets

Differential WBC (% and absolute counts) of
Neutrophils
Lymphocytes
Monocytes
Eosinophils
Basophils

Coagulation^c

Prothrombin time (PT)
Activated partial thromboplastin time (aPTT)
International normalized ratio (INR)

Urinalysis^a

Specific gravity
pH
Protein
Glucose
Ketones
Bilirubin
Urobilinogen
Blood
Nitrite

Clinical Chemistry

Sodium
Potassium
Bicarbonate (total CO₂)
Chloride
Calcium
Phosphorus
Glucose (random)
Creatine kinase
Gamma-glutamyl transferase (GGT)
Blood urea nitrogen (BUN)
Uric acid
Direct bilirubin
Total protein
Albumin
Total bilirubin
Alkaline phosphatase (ALP)
Aspartate aminotransferase (AST)
Alanine aminotransferase (ALT)
Creatinine

Ethanol testing^b
Urine drug screen^b
Hepatitis B surface antigen^c
Hepatitis B core antibody^c
Hepatitis C antibody^{c, d}
HIV antibody^c
FSH c, e

Abbreviations: FSH = follicle-stimulating hormone; HIV = human immunodeficiency virus; RBC = red blood cell; WBC = white blood cell.

- a Performed by dipstick. A microscopic examination will be run if blood, protein, nitrites or leukocyte esterase is positive.
- b Urine drug screen and ethanol (urine) level performed at screening and check-in.
- c Performed at screening only.
- d Participants with a positive hepatitis C antibody test result can have a confirmatory hepatitis C RNA test.
- e Postmenopausal women only.

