10.4. Appendix 4: Contraceptive and Barrier Guidance

Definitions:

Woman of Childbearing Potential (WOCBP)

A woman is considered fertile following menarche and until becoming postmenopausal unless permanently sterile (see below).

If fertility is unclear (e.g., amenorrhea in adolescents or athletes) and a menstrual cycle cannot be confirmed before first dose of study intervention, additional evaluation should be considered.

1. Women in the following categories are not considered WOCBP:

- a. Premenopausal female with 1 of the following:
 - hysterectomy
 - bilateral salpingectomy
 - bilateral oophorectomy
 - bilateral tubal ligation
 - bilateral tubal occlusion

For individuals with permanent infertility due to an alternate medical cause/congenital anomaly other than the above, (e.g., Müllerian agenesis, androgen insensitivity), investigator discretion should be applied to determining study entry.

Note: Determination can come from the site personnel's review of the participant's medical records, medical examination, or medical history interview.

- b. Postmenopausal female, defined as women with:
 - 12 months of amenorrhea for women >55 , with no need for FSH
 - 12 months of amenorrhea for women >40 years old with FSH ≥ 40 mIU/mL and no other medical condition such as anorexia nervosa and not taking medications during the amenorrhea (e.g. oral contraceptives, hormones, gonadotropin releasing hormone, anti-estrogens, selective ER modulators, or chemotherapy that induced amenorrhea).

Contraception Guidance:

Contraception is not required during this study.

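### Inclusion 7 requires participants to be not pregnant and admits premenopausal women after tubal ligation or occlusion, but the protocol's list of laboratory tests contains no pregnancy test

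*Protocol*

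**What the plan says.** **Entry condition.** Protocol Section 5.1, criterion 7, reads "This includes females who are not pregnant, non-lactating and either" infertile or postmenopausal. Absence of pregnancy is thus stated alongside non-childbearing status, as a condition of its own. The infertile route is "Infertile due to surgical sterilization (hysterectomy, bilateral oophorectomy or bilateral salpingectomy, bilateral tubal ligation, or bilateral tubal occlusion"), or another medical or congenital cause. Criterion 1 sets the age range at 18 to 65 years.

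**Who counts as not of childbearing potential.** Appendix 4 (Section 10.4) includes "Premenopausal female with 1 of the following", and the list that follows contains bilateral tubal ligation and bilateral tubal occlusion. A note allows the determination to come from "medical records, medical examination, or medical history interview". The appendix closes with "Contraception is not required during this study".

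**What is tested.** Section 8.2.4 points to Appendix 2 "for the list of clinical laboratory tests to be performed and the SoA (Section 1.3) for the timing and frequency". Appendix 2 (Section 10.2) is legible. It lists hematology, coagulation, chemistry, urinalysis, ethanol, drug screen, hepatitis B and C, HIV and FSH. FSH is restricted by footnote to screening and to postmenopausal women. Another footnote says "Urine drug screen and ethanol (urine) level performed at screening and check-in". No hCG or other pregnancy test appears in the list, in its footnotes, or elsewhere in the readable text of either document.

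**Why this population.** Section 4.2 explains the choice of women of non-childbearing potential by the drug's mechanism: it degrades the estrogen receptor, and "effects on the female reproductive organs are expected".

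**The concern.** The protocol states a condition of entry and names no laboratory test that confirms it. The gap falls on the eligible women for whom the condition has most content: premenopausal women who may have a uterus and functioning ovaries and whose sterility depends on a tubal procedure. The one reproductive test on the list, FSH, serves the postmenopausal route.

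The contrast with other criteria is plain. Drug and alcohol use are tested at screening and again at check-in, and hepatitis and HIV status at screening. Pregnancy status has no listed test at either visit.

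At stake is fetal exposure to an estrogen receptor degrader and a radiolabel. The mother would be a healthy volunteer, for whom Section 2.3 anticipates no benefit. The event is rare, but a pregnancy already present at dosing could be detected cheaply beforehand.

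**Working it through.** The plan gives no figure of its own on this point, so there is nothing to reproduce. The check has two parts.

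**1. Text comparison**

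| Question | Where | Answer |
|---|---|---|
| Is absence of pregnancy a stated condition? | Section 5.1, criterion 7 | Yes, in addition to infertility or menopause |
| Can a premenopausal woman after tubal ligation or occlusion enter? | Section 5.1, criterion 7; Appendix 4, item 1a | Yes, from age 18 |
| May an interview alone establish her sterilization? | Appendix 4, note to item 1a | Yes; records and examination are alternatives |
| Which document lists the tests? | Section 8.2.4 | Appendix 2; the Schedule of Activities (SoA) gives timing and frequency |
| Does the list contain a pregnancy test? | Appendix 2 and footnotes a to e | No |
| Must eligibility be confirmed, and are waivers allowed? | Section 8; Section 5 | Screening evaluations must confirm all criteria; waivers are not permitted |
| Is urine available at the right visits? | Appendix 2, footnote b | Yes, at screening and check-in |

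Following the readable text exactly, a site can enrol and dose such a woman with no laboratory check of the not-pregnant condition.

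**2. Size of the risk**

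Inputs:
- Planned maximum enrolment: 6 (Part 1) + 8 (Part 2) = 14 women, from Section 9.5. The sponsor may add replacements.
- Share entering by the tubal route: not in the documents. Assumed to be all 14, the worst case.
- Failure rate of tubal sterilization: not in the documents. Assumed 0.1% to 0.5% per woman per year.
- Time for which an early pregnancy goes unrecognised: not in the documents. Assumed 4 to 8 weeks.

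Expected pregnancies per year = 14 × annual failure rate:
- 14 × 0.001 = 0.014
- 14 × 0.005 = 0.07

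Chance of an undetected pregnancy at dosing, for the whole study ≈ expected pregnancies per year × weeks unrecognised / 52:

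| Annual failure rate | 4 weeks | 8 weeks |
|---|---|---|
| 0.1% | 0.014 × 4/52 = 0.0011 (0.11%) | 0.014 × 8/52 = 0.0022 (0.22%) |
| 0.5% | 0.07 × 4/52 = 0.0054 (0.54%) | 0.07 × 8/52 = 0.0108 (1.1%) |

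The range is about 0.1% to 1%. It scales directly with the share entering by this route: if half did so, every figure would halve.

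**The case against.** **The classification is deliberate.** Appendix 4 and inclusion 7 agree that women after tubal ligation or occlusion are not of childbearing potential. On that view absence of pregnancy follows from the classification and needs no test. This is a fair reading, but the protocol does not state it, and criterion 7 lists the two conditions separately. If the sponsor regards one as implied by the other, the text should say so.

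**Other checks exist.** A reader might infer that pregnancy is never checked before dosing, or that nothing in the protocol could detect it. The documents do not support that. Section 5 bases eligibility on history, examination, vital signs, laboratory tests and ECG. Section 8 requires screening evaluations to be reviewed against all criteria. Appendix 4 asks that further evaluation be considered when fertility is unclear. Appendix 2 lets the investigator add tests on judgment or where local rules call for them. What is missing is a listed laboratory confirmation. The additional tests are discretionary, so the gap remains.

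**Sterilization status is not always self-report.** Records and examination are also named as sources. Interview alone is permitted, not prescribed.

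**The SoA is redacted.** A pregnancy test listed only there cannot be excluded. Section 8.2.4 makes this unlikely, since it leaves only timing and frequency to the SoA. If one is there, Appendix 2 is incomplete and needs the same line added.

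**The contraception waiver adds little.** Part 2 participants stay in the unit until Day 9. Day 1 to Day 9 is 8 × 24 = 192 hours, or 192/30 = 6.4 to 192/25 = 7.7 half-lives at the 25 to 30 hours that Section 2.2.2 reports from patients. Part 1 participants normally stay until at least Day 12. The real question is a pregnancy already present at dosing.

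**Genotoxicity.** A reader might use the heading of Section 2.3.1 to raise the stakes. Its content is redacted and could be reassuring, so it supports nothing here.

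**Conclusion.** The point stands as a gap in laboratory confirmation of a stated entry criterion, for one identifiable subgroup. Inclusion 7, Appendix 2 and Appendix 4 together let premenopausal women in after tubal ligation or occlusion, require them not to be pregnant, and list no test of it. History, examination and records remain, so it would be wrong to say that the condition goes unchecked.

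The risk is small: about 0.1% to 1% for the whole study. That rests on the assumed failure rates and detection window, and on the worst case that all 14 women enter by this route. The case for a change does not depend on the exact figure. It rests on a serious, preventable harm and a very cheap check.

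The defect shown is confined to tubal ligation and occlusion. It does not justify extending testing to women after salpingectomy, or making medical records mandatory. Nothing here affects the estimate of absolute bioavailability, the mass balance or any other analysis.

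**What to change.** Add to Appendix 2 a urine hCG test for premenopausal participants who enter on the basis of bilateral tubal ligation or occlusion. Run it on the urine already collected at screening and check-in, and use the result to confirm the existing not-pregnant condition of inclusion 7. Testing at check-in as well as screening matters because up to 28 days may pass between screening and enrolment. List the timing in the SoA.

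Reconcile criterion 7, Appendix 2 and Appendix 4 so that the protocol says how the condition is verified and for which participants. If the SoA already holds such a test, the correction is to add it to Appendix 2.

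Cost: one added line in Appendix 2, matching wording in the related sections, and an inexpensive test for at most the 14 planned women and any replacements. No new visit or sample is needed. The downside is an occasional false positive, which would delay or exclude a participant.
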